7.1 DLT Analysis Set

The DLT analysis set will include DLT-evaluable subjects who have had the opportunity to be on treatment for at least 6 weeks from the initial dosing of study treatment and have received at least 2 doses of talimogene laherparepvec and 2 doses of

pembrolizumab in combination, or have a DLT during the DLT evaluation period after at least 1 dose of talimogene laherparepvec and pembrolizumab in combination.

7.2 Efficacy Analysis Set

The Efficacy Analysis Set (EAS) will be used for the primary efficacy analysis of the phase 1b. It is a subset of the Safety Analysis Set where subjects with locoregionally advanced disease with a recurrence < 3 months after prior platinum-containing curatively intended multimodal therapy are excluded.

7.3 Full Analysis Set

Secondary efficacy analyses for the phase 1b part of the study will be conducted on the Full Analysis Set (FAS) defined as all subjects who have received at least 1 dose of talimogene laherparepvec and 1 dose of pembrolizumab in combination. Efficacy will be analyzed with the FAS overall and excluding subjects in the EAS.

7.4 Safety Analysis Set

The Safety Analysis Set (SAS) will include all enrolled subjects (phase 1b) who received at least 1 dose of talimogene laherparepvec or pembrolizumab.

7.5 Biomarker Analysis Set

A Biomarker Analysis Set will be defined separately for each individual candidate biomarker. For exploratory and predictive analyses, the analysis set will include all treated (phase 1b) subjects with a baseline biomarker result and, for analyses of biomarker changes, the analysis set will include all treated (phase 1b) subjects that have a baseline and at least one subsequent biomarker result.

7.6 qPCR Suspicious Lesion Swab Analysis Set

The qPCR Suspicious Lesion Swab Analysis Set will include subjects who are enrolled (phase 1b), receive at least one dose of talimogene laherparepvec / placebo, and have at least one swab sample evaluable result from lesions suspicious to be herpetic in origin during the study. Evaluable samples are sample with either positive, BQL, or not detected results.

7.7 qPCR Blood Analysis Set

The qPCR Blood Analysis Set applies only to the phase 1b and will include treated subjects that have at least one post-dose blood sample evaluable result for qPCR testing of talimogene laherparepvec DNA.

7.8 qPCR Urine Analysis Set

The qPCR Urine Analysis Set applies only to the phase 1b and will include treated subjects that have at least one post-dose urine sample evaluable result for qPCR testing of talimogene laherparepvec DNA.

7.9 qPCR Exterior Occlusive Dressing Analysis Set

The qPCR Exterior Occlusive Dressing Analysis Set applies only to the phase 1b and will include treated subjects that have at least one post-dose exterior occlusive dressing surface swab evaluable result for qPCR testing of talimogene laherparepvec DNA.

7.10 qPCR Injected Lesion Analysis Set

The qPCR Injected Lesion Analysis Set applies only to the phase 1b and will include treated subjects that have at least one post-dose swab of an injected lesion with an evaluable result for qPCR testing of talimogene laherparepvec DNA.

7.11 qPCR Oral Mucosa Analysis Set

The qPCR Oral Mucosa Analysis Set applies only to the phase 1b and will include treated subjects that have at least one post-dose swab of oral mucosa with an evaluable result for qPCR testing of talimogene laherparepvec DNA.

7.12 qPCR Blood Clearance Analysis Set

The qPCR Blood Clearance Analysis Set applies only to the phase 1b and will include treated subjects that have at least one qPCR positive talimogene laherparepvec DNA blood sample, and at least one evaluable subsequent sample at any time during the same cycle.

7.13 qPCR Urine Clearance Analysis Set

The qPCR Urine Clearance Analysis Set applies only to the phase 1b and will include treated subjects that have at least one qPCR positive talimogene laherparepvec DNA urine sample, and at least one evaluable subsequent sample at any time during the same cycle.

7.14 Lesion Analysis Sets

The Injected Lesion Analysis Set includes any target lesion that was ever injected and the Uninjected Lesion Analysis Set includes any target lesion that was never injected. The Injected Lesion Evaluable and Uninjected Lesion Evaluable analysis sets will include the corresponding subset of target lesions with at least one post-baseline measurement prior to a censoring event, ie, non-study anticancer therapy, merged with another lesion, or resection (except if it is completely resected and pathology indicates

absence of malignant cells). If a lesion splits, the sum of the length of the split lesions will be added together prior to analysis.

8. Interim Analysis and Early Stopping Guidelines

8.1 Interim Analyses

DLT interim safety analyses are planned and conducted by the study team for the phase 1b with data being reviewed by a DLRT.

8.1.1 DLT Safety Analysis (Phase 1b)

Up to 3 planned safety interim analyses will occur during the phase 1b to evaluate the incidence of DLT according to timing/rules described in protocol Table 1 (Section 3.1.1). At each interim analysis, a DLT listing will be generated. The number and percentage of subjects with DLTs will be tabulated in a summary table among DLT-evaluable subjects. DLT evaluations will be based on the DLT Analysis Set. Data will be reviewed by a DLRT.

9. Data Screening and Acceptance

9.1 General Principles

The objective of the data screening is to assess the quantity, quality, and statistical characteristics of the data relative to the requirements of the planned analyses.

9.2 Data Handling and Electronic Transfer of Data

The Amgen Global Study Operations-Data Management (GSO-DM) department will provide all data, with the exception of biomarker data, to be used in the planned analyses. This study will use the RAVE database. PD-L1 and HPV data will be transferred electronically to Amgen via secure server.

9.3 Handling of Missing and Incomplete Data

Every effort will be made to obtain complete data in the clinical study. Partial or missing dates of adverse events and concomitant medications will be imputed. Adverse events and disease-related events (DRE) with missing IP relatedness (AEs only), seriousness, or CTCAE severity grades will be included in analyses as long as the events qualify for the reporting period. Events with missing relatedness (AEs only), seriousness, or severity grades will be excluded from corresponding treatment-related, serious, and worst grade analyses, respectively. If an AE or DRE end date is completely missing and the death date is available, the end date will be imputed with the death date. Details of the imputation algorithm for partial or missing dates, including death dates, are provided in [REDACTED] [Section 13](#).

9.4 Detection of Bias

Lack of protocol compliance may introduce potential bias in the estimation of protocol endpoints. All important protocol deviations (IPDs) will be reported, documented and stored in eClinical (a clinical trial management system). IPD reports will be produced using Cognos by the study manager and will be regularly reviewed in the study team's IPD review meetings as well as before analysis.

9.5 Outliers

Descriptive statistics will be used to identify potential outliers for key variables. Suspected outliers will be included in all analyses unless there is sufficient scientific justification to exclude them.

9.6 Distributional Characteristics

All binary endpoints will be assumed to follow a binomial distribution. The KM estimates for the probability of time-to-event endpoints are based on non-parametric methods.

Time to event endpoints will be evaluated with the non-parametric log-rank test.

9.7 Validation of Statistical Analyses

Programs will be developed and maintained, and output will be verified in accordance with current risk-based quality control procedures.

Tables, figures, and listings will be produced with validated standard macro programs where standard macros can produce the specified outputs.

The production environment for statistical analyses consists of Amgen-supported versions of statistical analysis software; for example, the SAS System version 9.4 or later.

10. Statistical Methods of Analysis

10.1 General Principles

For the phase 1b part of the study, the DLT Analysis Set will be used to summarize the subject incidence of DLT and, unless specified otherwise, the SAS will be used for all analyses of safety. Safety may also be analyzed using the EAS. The primary analysis of efficacy for the phase 1b will be based on the EAS with secondary analyses based on the FAS overall and excluding subjects in the EAS.

In principle, summary statistics including mean, standard deviation, median, first and third quartiles, will be provided for continuous variables. Frequency and percentage will be summarized by treatment arm for binary and categorical variables. Proportions and the corresponding 95% confidence intervals will be based on normal approximations and

the treatment comparison will be based on a Cochran-Mantel-Haenszel test. Exact tests will be considered for subgroup analyses when the cell size is considered small.

Time to-event endpoints will be estimated using the KM method.

Descriptive statistics will be provided for efficacy, safety, talimogene laherparepvec DNA, and biomarker endpoints as appropriate

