For a full list of study procedures, including the timing of each procedure, please refer to [Section 7](#) and the Schedule of Assessments ([Table 5](#), [Table 6](#), and [Table 7](#)).

Statistical Considerations:

Sample size consideration:

For phase 1b, a maximum of 18 DLT-evaluable subjects will be enrolled to assess the DLT profile of the combination therapy based on a sequential stopping rule. If > 18 subjects receive the combination they will contribute to the overall safety analysis, but only the first 18 DLT-evaluable will be considered in the decision to declare the combination safe. Subjects may be replaced if they are not evaluable for DLT to obtain 18 DLT-evaluable subjects. An expansion cohort of up to an additional 22 treated subjects will be enrolled so there will be approximately 40 treated subjects in total to estimate the efficacy of the combination of talimogene laherparepvec with pembrolizumab.

For phase 3, the primary endpoint is OS. A hazard ratio ([HR] talimogene laherparepvec with pembrolizumab vs placebo with pembrolizumab) of 0.7 for OS is hypothesized in the FAS(G). The overall 2-sided Type 1 error rate is 0.05. The event goal for OS to achieve 90% power for a 2-sided 0.05 significance level test is 336. Assuming approximately 75% of subjects have an OS event at the time of OS primary analysis, the sample size is estimated to be 450 (225 per arm). The OS event goal is adjusted for the interim efficacy analysis but not for the interim futility assessment; however, the power loss due to futility is < 1% if considered binding.

Planned method of analyses:

For the Phase 1b part of the study, the DLT analysis set will be used to summarize the subject incidence of DLT for the study and, unless specified otherwise, the safety analysis set (SAS) will be used for all other analyses of safety endpoints including incidence of treatment-emergent and

treatment-related adverse events. Summaries of the incidence of DLTs will be provided. Descriptive statistics will be provided for efficacy, safety, talimogene laherparepvec DNA, and biomarker endpoints as appropriate.

Efficacy endpoints will be summarized using the Efficacy Analysis Set (EAS) and FAS. The subject incidence for binary response endpoints will be summarized with an associated 95% confidence interval (CI). Duration of response (DOR) among responders, and other time-to-event endpoints will be estimated using the Kaplan-Meier method.

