10.2 Sample Size Considerations

10.2.1 Sample Size Considerations for Phase 1b

In testing for the null hypothesis H_0 that the combination of talimogene laherparepvec and pembrolizumab has a DLT rate $\leq 10\%$ versus the alternative hypothesis (H_a) that the true DLT rate is $\geq 33\%$, the sample size goal is to have $\geq 80\%$ power for a 1-sided $\leq 10\%$ significance level test to reject H_0 when H_a is true ([Goldman AI, 1987](#)).

With up to 3 safety interim analyses, the sequential stopping rules shown in [Table 1 \(Section 3.1.1\)](#) gives 81.6% power for a 7.7% 1-sided significance level test. A maximum of 18 DLT-evaluable subjects will be enrolled. If > 18 subjects receive the combination they will contribute to the overall safety analysis, but only the first 18 DLT-evaluable will be considered in the decision to declare the combination safe. Subjects may be replaced if they are not evaluable for DLT to obtain 18 DLT-evaluable subjects (eg, a subject did not receive study treatment, or ended the study treatment before completion of DLT evaluation period for a reason other than experiencing a DLT). The null hypothesis may be accepted and the combination declared safe prior to 18 DLT-evaluable subjects if it can be definitively determined that the stopping rule will not be exceeded with additional subjects.

An expansion cohort of up to an additional 22 treated subjects will be enrolled so there will be 40 treated subjects in total. The decision to proceed to phase 3 will consider safety data in all treated subjects and efficacy among all treated subjects excluding those with locoregionally advanced disease with disease progression or recurrence < 3 months after prior platinum-containing curatively intended multimodal therapy. The efficacy analysis is expected to include approximately 27 subjects. The decision to proceed to phase 3 will consider, for example, long-term tolerability and minimum efficacy consistent with pembrolizumab monotherapy historical data.

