- An audit-based Blind Independent Central Review (BICR) was added to assess the consistency of investigator- and BICR-assessed treatment effects for RECIST v1.1 ORR and PFS.

- The definition of the phase 3 primary efficacy and safety analysis sets, primary completion, and end of trial were revised to maintain the study's statistical considerations.
- Updated language on disease related events and reporting procedures – per internal Amgen recommendations.
- Updated language on disease related events and reporting procedures to align across program.
- Made minor administrative changes, text clarifications, and edits throughout the protocol.

Amendment 2

Protocol Title: A Phase 1b/3 Multicenter, Randomized Trial of Talimogene Laherparepvec in Combination With Pembrolizumab for the Treatment of Subjects With Recurrent or Metastatic Squamous Cell Carcinoma of the Head and Neck

Amgen Protocol Number (Talimogene Laherparepvec) 20130232

Rationale:

This protocol is being amended to:

- Update eligibility criteria triggered by recent safety signal – carotid blowout syndrome, and efficacy signal – lack of benefit in primary refractory patients with progressive disease within 3 months of curative intent multimodality therapy.
- Remove progression free survival as a primary endpoint for phase 3 and make it a secondary endpoint, along with CRR
 - The decision to forego of PFS as a dual primary endpoint hinged upon a few factors which included: the recent outcome of CHECKMATE 141 which led to approval of nivolumab based upon OS and also the final approval of pembrolizumab which is dependent upon OS from KEYNOTE 040. Considering the fact that OS is a superior outcome measure of a treatment over PFS especially in a poor prognosis disease and that PFS is not always a surrogate for OS, combined with the precedent set by nivolumab approval on OS, we felt that PFS did not have a truly meaningful role in the assessment of the efficacy of TVEC+pembrolizumab in second line head and neck cancer as well as for regulatory purposes.
- Add the use of irRECIST investigator assessment for response assessments and remove RECIST 1.1 central review.
- Update QOL/PRO wording and elevation of QLQ C30-3L to secondary endpoint from exploratory.
- Update statistical methods to justify the endpoint changes and also to introduce OS IA and futility analyses.
- To add more detail around go no go decision from Phase 1b to 3.
- Add additional pembrolizumab background information.

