10.5.2 Analyses of Secondary Efficacy Endpoints

10.5.2.1 Phase 1b

The primary analysis of efficacy for the phase 1b will be based on the EAS, with secondary analysis based on the FAS overall and excluding subjects in the EAS. All endpoints of the phase 1b will be descriptively analyzed.

The main efficacy endpoint in the phase 1b for the phase 3 decision will be the iORR with or without confirmation of response. Given the observed iORR in the Efficacy Analysis Set, the Bayesian posterior probability will be calculated that the true combination iORR exceeds the expected ORR for pembrolizumab by an absolute amount (δ). The expected iORR for pembrolizumab in the study population with 9 weeks minimum potential follow-up is approximately 11% and will be represented by a $\text{beta}(2.2, 17.8)$ distribution with mean 0.11 and precision 20.0. The iORR for the combination will be represented by a $\text{beta}(0.2, 1.8)$ distribution with mean 0.11 and precision 2.0. Given the observed iORR, the posterior probability will be calculated for a δ increase from 0% to 30% in 5% increments as well as a 90% credible region for δ (see [REDACTED]).

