10.6.8 Talimogene Laherparepvec DNA

10.6.8.1 Incidence of Detection of Talimogene Laherparepvec DNA in Lesions Suspected to be Herpetic in Origin

Phase 1b

The number and proportion of subjects with positive qPCR for talimogene laherparepvec DNA detection in any swab of a lesion suspected to be herpetic in origin will be calculated based on the qPCR Suspicious Lesion Swab Analysis Set. An exact 95% CI for the binomial proportion will be calculated ([Clopper & Pearson, 1934](#)).

Individual subjects having a positive qPCR results for talimogene laherparepvec DNA detection will be reviewed.

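### The SAP's normal-approximation 95% CIs for proportions break down at the small counts phase 1b is likely to produce

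*SAP*

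**What the plan says.** SAP 10.1 gives the general rule: "Proportions and the corresponding 95% confidence intervals will be based on normal approximations". The same sentence is in protocol 10.5.1. In both places it continues into a Cochran-Mantel-Haenszel comparison of treatments, although phase 1b has one arm.

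The protocol synopsis (planned method of analyses, phase 1b) commits to the intervals: "The subject incidence for binary response endpoints will be summarized with an associated 95% confidence interval (CI"). The sets named there are the EAS and the FAS. SAP 7.3 adds a third: "Efficacy will be analyzed with the FAS overall and excluding subjects in the EAS".

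SAP 10.5.2.1 and 10.5.3.1 name no other interval method for the response endpoints, and SAP 10.5.1.1 names none for DLT incidence. SAP 10.6.8 does so for the viral DNA and virus endpoints: "An exact 95% CI for the binomial proportion will be calculated", citing Clopper and Pearson. The remaining sentence on exact methods in SAP 10.1 concerns tests, applies to subgroups and is optional.

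On size, protocol 10.2.1 says "The efficacy analysis is expected to include approximately 27 subjects" out of 40 treated, with at most 18 DLT-evaluable. On the rate, SAP 10.5.2.1 says "The expected iORR for pembrolizumab in the study population with 9 weeks minimum potential follow-up is approximately 11" percent.

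**The concern.** A normal-approximation interval needs a reasonable number of events, and this plan expects few. At the reference rate the EAS would yield about 0.11 × 27 = 3 responders, and complete responses can only be as many or fewer.

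The FAS excluding the EAS is the group with recurrence less than 3 months after curative-intent therapy. The Amendment 2 rationale reports for them "lack of benefit in primary refractory patients with progressive disease within 3 months of curative intent multimodality therapy", so zero responders there is a realistic outcome.

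The sponsor decided not to proceed to phase 3 (SAP 11), so the study report rests on phase 1b, and these intervals are the stated precision of its response results. An interval of 0% to 0%, or one whose upper limit is too low, tells the reader that the data exclude rates they do not exclude.

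**Working it through.** **Inputs**
- n = 27 (EAS), 40 (treated) and 18 (maximum DLT-evaluable), from protocol 10.2.1.
- n = 40 - 27 = 13 for the FAS excluding the EAS. This is derived, not stated. It is approximate because 27 and 40 are approximate and because the EAS is defined as a subset of the SAS rather than of the FAS.
- Reference iORR 11%, represented by beta(2.2, 17.8), from protocol 10.2.1 and SAP 10.5.2.1. Mean: 2.2/(2.2 + 17.8) = 0.11.
- DLT null rate 10%, from protocol 10.2.1.
- Assumption: normal approximation means the Wald interval, p ± 1.96 × √(p(1 - p)/n) with p = x/n.

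**The plan's own figures.** Protocol 10.2.1 displays observed iORRs from 3/27 to 14/27. 3/27 = 11.1% and 14/27 = 51.9%, as printed.

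**When Wald fails**
- With x = 0 the standard error is 0, so the interval is 0% to 0% at every n.
- The lower limit is negative when x < 3.84 × (1 - x/n). For x = 1 this holds for n > 1.35, for x = 2 for n > 4.17 and for x = 3 for n > 13.70. For x = 4 or more it never holds.
- From n = 13 to 40 with x = 1 to 3 there are 28 × 3 = 84 cases. The limit is negative in 83; the exception is 3/13.

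**Intervals.** For 3/27: √(0.1111 × 0.8889/27) = 0.0605, and 1.96 × 0.0605 = 0.1185, giving 0.1111 ± 0.1185.

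| x/n | Wald | Clopper-Pearson | Wilson |
|---|---|---|---|
| 0/13 | 0 to 0% | 0 to 24.7% | 0 to 22.8% |
| 0/18 | 0 to 0% | 0 to 18.5% | 0 to 17.6% |
| 1/27 | -3.4 to 10.8% | 0.1 to 19.0% | 0.7 to 18.3% |
| 3/27 | -0.7 to 23.0% | 2.4 to 29.2% | 3.9 to 28.1% |
| 3/40 | -0.7 to 15.7% | 1.6 to 20.4% | 2.6 to 19.9% |
| 14/27 | 33.0 to 70.7% | 31.9 to 71.3% | 34.0 to 69.3% |

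The lowest outcome the protocol displays, 3/27, already has a negative Wald limit.

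**How often.** At a true rate of 11% and n = 27, P(X ≤ 3) = 0.655. At n = 13 and 11%, P(X = 0) = 0.89^13 = 0.22. The latter assumes the pembrolizumab reference rate applies to that set; a lower rate makes zero more likely.

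**Coverage.** This is the sum of binomial probabilities over every x whose interval contains the true rate.

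| n | True rate | Wald | Clopper-Pearson | Wilson |
|---|---|---|---|---|
| 27 | 10% | 93.8% | 98.5% | 95.3% |
| 27 | 11% | 80.7% | 97.6% | 97.6% |
| 18 | 10% | 84.3% | 99.4% | 97.2% |
| 13 | 10% | 73.9% | 99.4% | 96.6% |
| 13 | 11% | 77.0% | 99.0% | 95.4% |

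The fall between 10% and 11% at n = 27 arises because the Wald upper limit for 1/27 is 10.8%. Above that rate, samples with one responder no longer cover the truth.

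Because single points are erratic, coverage was also averaged. For each x, the beta-binomial probability was multiplied by the posterior mass inside the interval, and the products summed. Over beta(2.2, 17.8):
- n = 27: Wald 82.1%, Clopper-Pearson about 98%, Wilson 95.6%.
- n = 13: Wald 67.9%, Clopper-Pearson about 99%, Wilson 95.6%.

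Over true rates spread evenly across the displayed range of 11.1% to 51.9% at n = 27, Wald coverage runs from 81% to 96% with a mean of 92%.

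**The case against.** - **The SAP does not say Wald.** The Wilson interval also rests on a normal approximation and has none of these defects. That is true, and every Wald figure here depends on the reading. But Wald is the ordinary meaning of the words. A plan that allows both readings has left the method open, and naming Wilson would settle the point.
- **The 11% is the pembrolizumab reference at 9 weeks, not the rate hoped for.** At n = 27 the chance of 3 or fewer responders falls to 41% at a true rate of 15%, 18% at 20% and 2% at 30%, and at 14/27 the methods nearly agree. This stands. Disease control and overall adverse-event incidence are not low-rate endpoints either. But a pre-specified method should work at the plan's own reference rate, and complete response can be no more frequent than overall response.
- **Nothing is decided on these intervals.** This also stands. Tolerability follows the counts in protocol Table 1, and the phase 3 decision was based on a Bayesian posterior and has been taken. Counts are reported, so a reader could recompute an interval.
- **No interval is expressly required for DLT incidence or for lesion-level rates.** Correct. The n = 18 figures matter only if a DLT interval is given under the general rule.

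Cutting the lower limit at zero would be no repair: the upper limit would stay too low, 10.8% against 19.0% for 1/27.

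**Conclusion.** The concern holds. As written, the SAP applies a normal-approximation interval to response rates in sets of about 13 to 40 subjects, while already specifying a suitable exact method for other endpoints in the same sets. Under the Wald reading, and with true rates distributed as the plan's own pembrolizumab beta distribution, a nominal 95% interval covers about 82% of the time at n = 27 and 68% at n = 13. With 0 to 3 events the interval is visibly defective in every case but 3/13.

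The problem is small at high response rates, and its effect is confined to how precision is reported. It should be fixed because the reported error bars would be wrong in likely outcomes and the change is trivial.

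**What to change.** In SAP 10.1, replace the normal-approximation rule with the Clopper-Pearson interval already used in SAP 10.6.8, or name the Wilson score interval. Apply it to subject-level iORR, iCRR, iDCR, ORR, CRR and DCR, to the subject incidence of L-CR and L-PR and, if an interval is shown, to DLT incidence. Delete the treatment-comparison clause for phase 1b.

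If intervals are reported for lesion-level L-ORR, L-CR or L-PR, use ones that account for clustering within subject. A phase 1b subject can have up to 10 target lesions, while SAP 9.6 says "All binary endpoints will be assumed to follow a binomial distribution". The size of that effect depends on a within-subject correlation the documents do not give.

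The cost is one sentence and a macro option. Clopper-Pearson is conservative (about 98% averaged coverage at n = 27) and somewhat wider; Wilson is closer to 95%. The SAP also covers the follow-up and final analyses, so the change has outputs to apply to.
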